1.0 Background and Purpose

The misuse of and addiction to opioid medications has become the most rapidly increasing drug problem in the US, which has consequences for pregnant mothers and their babies. The prevalence of maternal opioid drug use at the time of delivery in California is approximately one percent. The neonatal abstinence syndrome (**NAS**) is a constellation of narcotic drug withdrawal symptoms that develops in 42 to 94 percent of infants born to narcotic dependent mothers. There are no preventative treatments for this severe syndrome, which can result in a prolonged hospitalization and treatment in a neonatal intensive care unit.

Based upon a genetic discovery, we demonstrated that administration of a 5-HT3 antagonist (ondansetron) prevented the symptoms of narcotic drug withdrawal in experimental studies in mice and in humans. From this, we hypothesize that ondansetron administration to pregnant narcotic-using mothers just prior to delivery, followed by a 3 to 5-day period of ondansetron

administration to the neonate, could reduce the incidence or severity of NAS symptoms. Ondansetron is a broadly utilized drug with a substantial safety record in pregnant women. We now understand the pharmacokinetics of ondansetron at birth based on PK analysis of placental and neonatal blood samples in babies whose mothers' were given ondansetron prophylactically prior to cesarean delivery (Aim 1 of the protocol, Prevention of Neonatal Abstinence Syndrome). In this study, (Aim 2) we will conduct a multi-center, randomized, double blind, and placebo-controlled trial to determine whether ondansetron treatment will reduce the incidence (percentage of infants requiring narcotic drug treatment) or severity (total amount of narcotic drug required, length of hospitalization, symptom severity scores) of NAS in babies born to narcotic-using mothers.

This project tests a very novel approach for preventing an important pregnancy-related complication of narcotic drug abuse. If a brief period of ondansetron administration to the mothers that use narcotic drugs, and to their babies, can prevent or ameliorate the development of narcotic drug withdrawal symptoms in neonates, this would reduce human suffering and the growing societal cost of opiate abuse.

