6. Follow-up calls/visits: a research team member will call the mother of the baby once they have been discharged home, if the baby is discharged prior to Day 15 of their life. We want to follow up on the babies and learn how they are doing and make sure they are not going into "Delayed" NAS. For babies who are discharged early it is more likely they could go into delayed NAS and that is why we plan to call the mothers daily, for up to 10 days after the baby takes their last dose of study medication, to ask about their baby's status. We are interested in how the baby is feeding, are they breast or bottle feeding the baby, what is the baby's mood (crying excessively, fussy, agitated), sleeps for how many hours after feeding, sneezing a lot, sweating, vomiting, gaining weight, loose stools or watery stools, etc. We also need to ask the mother all the medications she is taking, if she is breastfeeding her baby, since we know these medications will enter the baby's system through the breast milk. If a baby is not discharged before day 15 of their life, the research team member will visit the baby in the hospital daily, for 10 days after their last dose of study drug, to check on the status of the baby from the clinical team caring for the baby. If the mother is home while the baby remains hospitalized, the research team member will also call the mother on a daily basis to maintain contact and to ask the mother all the medications she is taking if she is breastfeeding her baby (we know these medications may enter the baby's system through the breast milk).

7. The final follow-up call (or visit if the baby is still in the hospital) will occur approximately 30 days after the baby's last dose of study medication; this call (or visit) will be to determine if any previously reported adverse events have resolved and/or if any new adverse events have occurred since the last follow-up call or visit.

The primary endpoint will be the incidence of NAS in enrolled neonates and will be measured by the need for pharmacologic treatment for the symptoms of NAS (Morphine). The secondary endpoint of the severity of NAS will be measured by the length of the hospitalization (birth to discharge), the total dose of narcotic required to treat the symptoms of NAS, and the need to include barbiturates in the treatment of symptoms of NAS.

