AIM 2- Prevention of Neonatal Abstinence Syndrome

Statistical Analysis Plan

NCT01965704

March 30, 2022

Only infants who received at least one dose of study medication and met the inclusion criteria were included in the efficacy analysis. All infants and mothers who were allocated and received at least one dose of study medication were included in the safety analysis. Power analysis effect size was based upon NPOW response data that was obtained from the healthy opioid-naïve adult volunteers under controlled conditions. In that study, there was a difference of 2.38 between the means of the control and ondansetron-treated withdrawal responses, with standard deviations of 2.23 and 0.89, respectively. Based upon these numbers, 13 patients per treatment arm would have 90% power to ensure that a treatment difference (ondansetron vs. control) could be detected at the $p=0.05$ level. However, because of the very large of differences between opioid-naïve adults analyzed under experimentally controlled conditions and infants that are exposed *in utero* to opioids, the actual relative effect size of ondansetron treatment was assumed to be 25-33% of that estimated from the pilot data in normal subjects. This revised effect size estimate provided 45 infants in each arm to provide the same statistical power. For the categorical outcomes in the primary and secondary endpoints (the fraction of infants requiring pharmacologic therapy with morphine and the need for adjunctive phenobarbital or clonidine therapy), Fisher's Exact test was used to perform the analysis of independence. Because the need for morphine was not impacted by the sex of the neonates or by the race/ethnicity of the mother, these stratification factors were not corrected for in the analysis of primary outcome.

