The null hypothesis for the Fisher's Exact test was that the need for morphine treatment and study drug allocation were independent. The continuous outcomes of secondary endpoints were examined using the two-sided Wilcoxon Rank-Sum test (equivalent to the Mann-Whitney test), where the null hypothesis is stated as the outcomes in the ondansetron and placebo arms are equal. Inclusion of neonates in the safety population was based upon receipt of ondansetron in any form (study drug administered to infant or exposure through maternal transfer). QTc values in the safety population were analyzed by two sample t-test to determine if the mean QTc of two groups were equal. All tests were two-sided, and the p-values obtained from statistical tests were compared with the significance level ($\alpha =0.05$) to determine whether null hypothesis could be rejected or retained. Statistical analyses were performed using R software (version 3.6.1).

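### At 25–33% of the pilot effect, 45 infants per arm does not give 90% power: on the pilot scale the SAP's own inputs need about 100–173 per arm

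*SAP*

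**What the plan says.** The SAP's power text takes its inputs from a study of healthy adult volunteers: "Power analysis effect size was based upon NPOW response data". It reports a difference in means of 2.38 with SDs of 2.23 (control) and 0.89 (ondansetron), and says that "13 patients per treatment arm would have 90% power" at the 0.05 level. It then scales the effect down for opioid-exposed infants: "the actual relative effect size of ondansetron treatment was assumed to be 25-33% of that estimated from the pilot data in normal subjects". From this it concludes: "This revised effect size estimate provided 45 infants in each arm to provide the same statistical power". No formula, revised SD or working is shown.

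The primary endpoint is on a different scale. Protocol section 2.1.1 says: "The primary endpoint will be the incidence of NAS in enrolled neonates and will be measured by the need for pharmacologic treatment". The SAP tests this binary outcome with Fisher's exact test. For inference, its last paragraph compares two-sided p-values with 0.05 "to determine whether null hypothesis could be rejected or retained".

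**The concern.** For a comparison of two means, the sample size at fixed power and alpha varies with the inverse square of the effect. Cutting the effect to a quarter or a third should multiply the sample size by roughly 16 or 9. The SAP multiplies it by about 3.5 (45/13).

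In the text available for review, this sentence is the only justification for 45 per arm. The SAP names no effect estimate or confidence interval for the primary outcome, only rejection or retention of the null. If the null is retained, the one statement in the plan about how informative that result is would be the 90% figure. If that figure is wrong, a null result looks far more conclusive than it is at the effect the SAP itself assumes.

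**Working it through.** **Inputs.** From the SAP's power text: difference 2.38; SDs 2.23 and 0.89; 90% power; alpha 0.05; infant effect 25–33% of the pilot effect. The SAP's last paragraph makes all tests two-sided. Protocol section 2.1.1 B gives 1:1 allocation. I assume that the pilot SDs carry over, because no others are given.

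**Standardised effect.** SD = √((2.23² + 0.89²)/2) = 1.698, so d = 2.38/1.698 = 1.402.

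**Step 1: the SAP's 13 per arm.** The normal approximation n = 2(1.960 + 1.282)²/d² gives 21.01/1.402² = 10.7, or 11. Noncentral-t power is:

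| n per arm | Pooled t | Unequal-variance (Welch) t |
|---|---|---|
| 12 | 90.7% | 89.2% |
| 13 | 92.9% | 91.8% |

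Under Welch, 13 is exactly the minimum. The SAP's first figure is confirmed.

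**Step 2: the same method at the reduced effect.**

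| Fraction of pilot effect | Difference | d | n per arm, normal approx. | n per arm, t and Welch | Power at 45 per arm (pooled / Welch) |
|---|---|---|---|---|---|
| 33% | 0.785 | 0.463 | 99 | 100 | 58.3% / 57.8% |
| 25% | 0.595 | 0.350 | 172 | 173 | 37.6% / 37.2% |

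These are 7.7 and 13.3 times 13 (100/13 and 173/13). They fall short of 9 and 16 because 33% is slightly less than a third of the way down in rounding terms and, mainly, because small-sample t-tests carry a penalty that inflates the 13.

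At 45 per arm, 90% power is reached only at 49% of the pilot effect (pooled t: fraction 0.493, d = 0.69, difference 1.17). The full planned enrolment of 120 pairs, or 60 per arm, would give about 71% at the 33% effect and 48% at the 25% effect.

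**Step 3: other readings** (n per arm for 90% power unless stated).

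| Reading | n per arm |
|---|---|
| Effect reduced *by* 25–33% | 21–26 |
| One-sided test | 81–141 |
| 80% power | 75–129 |
| SD 2.23 in both arms | 171–297 |
| SD 0.89 in both arms | 28–48 |

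Only the last range contains 45, but with that SD the full effect would need 5 per arm, which contradicts the stated 13.

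**Possible source of the 45.** Dividing 13 by the fraction itself, not its square, gives 13/0.33 = 39.4, 13/0.29 = 44.8 and 13/0.25 = 52. A linear scaling near the middle of the range would give 45. This is inference, and the conclusion does not depend on it.

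**Primary endpoint: illustration only.** Power for need for morphine cannot be derived from the documents. Protocol section 1.0 says that NAS "develops in 42 to 94 percent of infants born to narcotic dependent mothers". *Assuming* a control rate of needing morphine somewhere in that range, exact two-sided Fisher power at 45 per arm reaches 90% as follows:

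| Assumed control rate | Treated rate for 90% power | Absolute fall (points) |
|---|---|---|
| 42% | 10.9% | 31.1 |
| 50% | 16.8% | 33.2 |
| 60% | 24.7% | 35.3 |
| 68% | 32.0% | 36.0 |
| 80% | 46.0% | 34.0 |
| 94% | 66.2% | 27.8 |

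**The case against.** The strongest reply is that the SAP does not define the metric of its effect size, and that one metric returns 45. If the percentage applies to the *squared* standardised effect, 25% of it is half the mean difference, and Welch then needs exactly 45 per arm (89.8% power at 44, 90.5% at 45). So it is too strong to say that no reading reaches 45. But this reading means detecting half the pilot difference, which is not how the SAP's wording reads. At 33% it gives 34 per arm, and scaling n by the inverse of the fraction is the same linear scaling suggested above as the likely slip.

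A second reading takes 25–33% as a relative reduction in the binary endpoint. From control rates of 90–94%, about 35–68 per arm would be needed (uncorrected two-proportion formula), which brackets 45. At 42–80% it would be 65–441. The SAP gives no control rate for the calculation, and it ties the percentage to the pilot data, not to an event rate.

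Three further points have some force. The SAP is dated March 2022 and written in the past tense, so the correction changes no p-value; it changes how a null result is read. A reader given the arm proportions could compute an interval, but the SAP does not call for one. The range used in the illustration describes developing NAS, not needing morphine, so the Fisher figures carry no weight in the conclusion.

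**Conclusion.** The concern holds. Under the ordinary reading of the SAP's wording, and by the method that reproduces its own 13 per arm, 25–33% of the pilot effect needs 173 to 100 infants per arm for 90% power. The stated 45 gives about 38–58%. This rests on the NPOW scale, two-sided alpha 0.05, 1:1 allocation and the pilot SDs applying to infants. The linear-scaling explanation is conjecture.

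Neither the stated 90% nor the corrected 38–58% is the power of the primary analysis. That analysis is Fisher's exact test on a binary outcome, and the plan specifies neither event rates nor a target difference for it.

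**What to change.** Leave enrolment unchanged. Replace the sentence on 45 per arm with:

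> On the continuous pilot (NPOW) scale, assuming the pilot SDs, 45 per arm has about 38–58% power at 25–33% of the pilot effect, and 90% power only at about 49% or more of it. This is not the power of Fisher's exact test on the binary primary endpoint (need for morphine), for which no event rates or target difference were specified.

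If the sponsor meant another metric, the calculation and the definition of the effect size should be shown instead. Report the primary result as an effect estimate with a confidence interval, and do not interpret a non-significant result as if the trial had 90% power.

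The cost is SAP and report wording plus one confidence interval. The test, analysis population and alpha stay as they are. The stated power becomes less favourable.

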1. Maternal blood for ondansetron concentration (PK) will be collected within 30 minutes of delivery (either pre- or post-delivery).
2. Maternal urine will be collected for toxicology analysis prior to delivery to identify possible polysubstance abuse (polysubstance use is not an exclusion criteria)
3. Once delivery is complete, the mother's participation will consist mainly of answering questions about her own medication use and the baby's feeding habits over the remainder of the study while the neonate participates in the study.

Neonatal Participant's Procedures:

1. The Modified Finnegan scoring system will be used to evaluate neonates for symptoms of NAS at each site involved in the study and is considered standard-of-care for babies who are at risk for NAS. Treatment with the study medication will continue for a maximum of five days (starting within approximately 4-8 hours after birth).
2. Treatment of NAS: morphine will be the first treatment choice before other treatment medication choices (opioid or non-opioid) for NAS symptoms. This is the standard-of-care at all participating sites. Each site involved has established guidelines for starting, advancing and weaning treatment for NAS. Any medication used to treat the symptoms of NAS will be noted as to name, dose, route, reason for dosage (Finnegan score or other reason) and time of administration. If the neonate develops nausea and clinical treatment of the nausea would include ondansetron then an alternate antiemetic should be considered. The infant may already have a full therapeutic level of ondansetron and additional dosage will not help treat the nausea. Ondansetron is not strictly contraindicated by this protocol as some neonates will have received placebo. For those infants that have been randomized to ondansetron, an additional dose of ondansetron will not be harmful.
3. 12-Lead ECG: all neonates, whether they are cared for in Well Baby Nursery or the NICU, will have a screening 12-lead ECG prior to their first dose of study drug and a follow-up 12-lead ECG within 2- 5 hours after each dose of study drug.

4. Umbilical cord blood (venous) will be collected at delivery and evaluated for ondansetron and ondansetron metabolite concentration. The standard of care at most hospitals is to discard the umbilical cord in the hospital biological waste system unless the parents have asked for it to be saved. We will only take these cord samples if the mother agrees to let us have them.

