4.3 Neonatal data

1. Gestational age, 2. Mode of delivery, 3. Birth weight, 4. Birth Length (height), 5. Neonatal co-morbidities, 6. Duration of hospital stay (birth to discharge), 7. Need for medical treatment of NAS, 8. Time from birth to initial pharmacological treatment of NAS, 9. Need for barbiturate treatment for NAS, 10. Duration of medical treatment of NAS, 11. Weight change during hospitalization, 12. Gender, 13. Modified Finnegan scores, 14. All 12-lead ECG results, 15. Frequency and duration of breast/bottle feeding in hospital and home after discharge, 16. Apgar 1min, Apgar 5 min 17. All medications used to treat NAS (drug name, dosage, route, reason for dosing, time & date), 18. pharmacokinetic blood results for ondansetron, 19. Date of birth, 20. Medical record number.

Data Security

Study team members at all sites will have access to the identifiable protected health information (PHI) of participants. During the data-collection phase of this study, all identifiable data will be kept in a locked environment. All electronic data will be encrypted and kept on a password-protected computer. A REDCap database will be designed and maintained by the study team for the compilation of all study data. This database meets all regulatory standards for safe and confidential storage and management of human subject research data. At the earliest possible time, after complete analysis and confirmation of accuracy of the data collected, all data will be de-identified.

A unique study number will be assigned to each participant. The code to link this number to PHI will be encrypted and kept in a password-protected computer. Tissue specimens for ondansetron levels will be labeled with this coded study number only and will not include any information that would link the sample to the participant. The urine toxicology screens will be analyzed in the respective hospital laboratories.

Due to the sensitive nature of the data collected and to protect the rights of the study participants, a Certificate of Confidentiality was obtained from the NIH on August 21, 2013.

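### The SAP's secondary outcome of phenobarbital or clonidine does not match the protocol's secondary endpoint of barbiturate need, and the SAP neither explains nor dates the difference

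*SAP*

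**What the plan says.** The endpoint paragraph at the end of the study procedures in protocol section 2.1.1 gives the severity endpoint three measures: length of stay from birth to discharge, total narcotic dose, and "the need to include barbiturates in the treatment of symptoms of NAS". Section 4.3, item 9, lists "Need for barbiturate treatment for NAS" as a separate data item. Item 17 of the same list records "All medications used to treat NAS (drug name, dosage, route, reason for dosing, time & date", so every drug given for NAS can be identified.

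On treatment, section 2.1.1 says that "morphine will be the first treatment choice before other treatment medication choices (opioid or non-opioid) for NAS symptoms". The protocol text available for this review does not name clonidine or phenobarbital.

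The SAP gives its categorical outcomes in one parenthesis: the fraction of infants needing morphine, and "the need for adjunctive phenobarbital or clonidine therapy". For these, "Fisher's Exact test was used to perform the analysis of independence". It adds that "All tests were two-sided", at a significance level of 0.05.

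**The concern.** One component of the secondary endpoint is defined by a drug class in the protocol and by two named drugs in the SAP, and one of those drugs is outside the class. If the SAP is followed as written, the comparison that the protocol specified may never be reported, and a different event would stand in its place without being marked as a change.

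The timing is undocumented. The SAP is written in the past tense. It justifies an unadjusted primary analysis by reporting that morphine need did not vary with the infant's sex or the mother's race or ethnicity. Whoever wrote that had seen outcome data. A reader therefore cannot treat the SAP's definition as prespecified on the strength of the SAP alone.

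**Working it through.** The plan states no figure that depends on this definition, so there is none to reproduce. The check is a comparison of definitions, followed by an illustration under assumed rates.

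**Step 1: classify infants under each definition** (SAP read as one combined outcome).

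| Drugs given for NAS | Protocol 2.1.1 and 4.3 | SAP |
|---|---|---|
| Morphine only | non-event | non-event |
| Morphine + phenobarbital | event | event |
| Morphine + clonidine, no barbiturate | non-event | event |
| Morphine + a barbiturate other than phenobarbital | event | non-event |

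The definitions disagree in two rows. The SAP is broader because it adds clonidine, and literally narrower because it names one barbiturate rather than the class.

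**Step 2: could the definition matter?** Inputs from the SAP: 45 infants per arm (its sample-size target), Fisher's exact test, two-sided 0.05. Assumed, because the documents give no rates: barbiturate need and clonidine-only need in each arm. Power is computed exactly as the sum over a and b of Bin(a; 45, p1) × Bin(b; 45, p2), taken over all tables with Fisher p ≤ 0.05.

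- Barbiturates alone, 20% on placebo against 10% on ondansetron: power 0.18.
- Clonidine-only use adds 10 points in both arms (30% against 20%): power 0.13.
- Clonidine-only use of 10% on placebo is also halved (30% against 15%): power 0.30.

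With ondansetron halving barbiturate need, placebo barbiturate rates of 10–30% and clonidine-only rates of 5–15%, power runs from 0.06 to 0.30 for barbiturates alone and from 0.05 to 0.55 for the combined outcome. The definition can move the result in either direction.

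**Step 3: share of events affected.** Assume 15% barbiturate need and 5–20% clonidine-only need. Expected events per arm go from 45 × 0.15 = 6.75 to between 45 × 0.20 = 9.0 and 45 × 0.35 = 15.75. Clonidine-only events are then 0.05/0.20 = 25% to 0.20/0.35 = 57% of the total.

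**Step 4: type I error.** Under the same rates with no treatment effect, the chance that at least one of the two nested definitions reaches p<0.05 is 4.0–5.2%, against about 2.5% for barbiturates alone. The starting value is low because Fisher's test is conservative. The range lies at about the nominal 5%.

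**The case against.** The strongest reply is that phenobarbital or clonidine is the better measure of the intended idea, namely that morphine was not enough. The protocol says that each site follows its own NAS guideline. If some sites add clonidine where others add phenobarbital, counting barbiturates alone scores infants by site habit. This stands as far as it goes. A reader might infer that the combined outcome is the more site-dependent of the two, but the documents do not support that. The same guidelines govern both drugs, the guidelines themselves are not in the material available, and randomised, double-blind allocation makes site practice mainly a source of noise rather than of bias between arms.

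Second, the SAP never calls the outcome a composite, and its wording could mean two separate tests. That is possible. Phenobarbital would then be tested alone, close to the protocol's endpoint, but clonidine would still be an added outcome without explanation, and the SAP would still need to say which is meant.

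Third, a reader might infer that having two definitions inflates type I error, or that clonidine was added because of the results. Step 4 does not support the first: the rate stays at about 5%, and it rests on assumed drug use. The second is not shown either. The SAP's date is that of the document, and nothing says when clonidine entered the definition.

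Finally, the protocol's purpose statement (section 1.0) lists severity measures without barbiturates. The endpoint paragraph in section 2.1.1 does include them, and section 4.3 collects them, so the measure is part of the protocol's endpoint.

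**Conclusion.** The mismatch is real and follows from the text alone. On the natural reading, the SAP tests a different event from the protocol's, lists no test of barbiturate need, and gives no reason. Nothing in it shows that the change came before outcomes were known.

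Its reach is modest: one of three components of the secondary endpoint. The primary endpoint, the sample size and the significance level do not depend on it. Its effect on the result cannot be sized from the documents; the illustration shows only that it could go either way. The finding assumes that the parenthesis in the SAP describes one combined outcome. If two tests were meant, it shrinks to an unexplained added outcome and an unclear sentence. The change should still be made, because it restores a protocol-specified analysis that the SAP does not clearly deliver.

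**What to change.** In the SAP paragraph on categorical outcomes:

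- Name need for barbiturate treatment of NAS as the protocol-specified component and test it with Fisher's exact test.
- Report phenobarbital or clonidine beside it, labelled as an outcome added after the protocol. State whether it is one combined outcome or two separate tests, and when and why it was added.
- Tabulate each adjunct drug by arm from the medication records in protocol section 4.3, item 17.

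The cost is a few sentences, one extra Fisher test and a table row. No new data are needed and patient care is unaffected. The downside is one more secondary comparison to report, which the labelling makes plain.
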